3.3.2.11 Corrected QTc Prolongation

The effect of orally administered cabozantinib 140 mg qd on QTc interval was evaluated in a placebo-controlled study in subjects with MTC. A mean increase in QTcF of 10-15 ms was observed after 4 weeks after initiating cabozantinib treatment. A concentration-QTc relationship could not be definitively established. Changes in cardiac wave form morphology or new rhythms were not observed. No cabozantinib-treated subjects in this study had a QTcF > 500 ms.

Unless otherwise specified in certain protocols, only subjects with a baseline QTcF \leq 500 msec are eligible for cabozantinib research studies. Cabozantinib should be used with caution in subjects with QT prolongation risk, a history of QT interval prolongation, or who are taking antiarrhythmics or drugs known to prolong the QT interval. Concomitant treatment with strong CYP3A4 inhibitors, which may increase cabozantinib plasma concentrations, should be avoided.

If at any time on study there is an increase in QTcF to an absolute value $>$ 500 ms or an increase of $>$ 60 ms above baseline, two additional ECGs must be performed with intervals not less than 3 min apart within 30 min after the initial ECG.

If the average QTcF from the three ECGs is $>$ 500 ms or increased by $>$ 60 ms above baseline, the following actions must be taken:

- Withhold study treatment
- Immediately notify the Sponsor
- Hospitalize symptomatic subjects (eg, with palpitations, dizziness, syncope, orthostatic hypotension, a significant ventricular arrhythmia on ECG) for a thorough cardiology evaluation and management
- Consider cardiology consultation for asymptomatic subjects for evaluation and management
- Check electrolytes, especially magnesium, potassium and calcium; correct abnormalities as clinically indicated
- Check concomitant medications for any medication that may have contributed to QT prolongation, and if possible, discontinue these medications (<http://www.qtdrugs.org>)
- Repeat ECG triplicates hourly until the average QTcF is \leq 500 msec, or otherwise determined by consultation with a cardiologist or appropriate expert.

Subjects with QTc prolongation and symptoms must be monitored closely until the QTc elevation and symptoms have resolved. Study treatment may be restarted at a reduced dose level if all of the following conditions are met:

- Symptoms are determined to be unrelated to the QT interval prolongation
- The QTcF value $>$ 500 ms or increase of $>$ 60 ms above baseline is not confirmed according to protocol procedures
- Study treatment has been interrupted through a minimum of 1 week following the return of the QTcF to \leq 500 msec or return to \leq 60 ms above baseline.
- QT prolongation can be unequivocally associated with an event other than cabozantinib administration and is treatable/has been resolved
- Sponsor has reviewed all available information and has agreed to the continuation of study treatment

Following reinitiation of study treatment, ECGs must be repeated weekly for 2 weeks, then every 2 weeks for 1 month, then according to the protocol-defined time points.

All study treatment must be permanently discontinued if either of the following applies:

- Cardiac evaluation confirms that symptoms are the consequence of QT interval prolongation
- Recurrence of QTcF prolongation (confirmed by central ECG lab) after reinitiation of study treatment at a reduced dose

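### Section 3.3.2.11: for a QTc hold mandated by the triplicate ECG, the restart list contradicts its own trigger, and one of the two permanent-stop triggers cites a central ECG lab described nowhere else

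*Combined protocol and SAP*

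**What the plan says.** Section 3.3.2.11 sets out four steps.

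- **Check.** After a first QTcF above 500 ms or more than 60 ms above baseline, the rule is that "two additional ECGs must be performed with intervals not less than 3 min apart within 30 min after the initial ECG".
- **Hold.** The trigger begins "If the average QTcF from the three ECGs is" and applies the same two thresholds to that average. The first required action is "Withhold study treatment"; the sponsor must also be told at once.
- **Restart.** "Study treatment may be restarted at a reduced dose level if all of the following conditions are met". The five conditions are: symptoms not due to the QT prolongation; the value over the same thresholds "above baseline is not confirmed according to protocol procedures"; a dosing break lasting at least a week after QTcF is back at 500 ms or less, or within 60 ms of baseline; a cause other than the study's kinase inhibitor, worded as "QT prolongation can be unequivocally associated with an event other than cabozantinib administration and is treatable/has been resolved"; and sponsor review and agreement. A schedule of repeat ECGs after restart follows.
- **Permanent stop.** Either of two triggers suffices. One is a cardiac evaluation that attributes the symptoms to QT prolongation. The other is "Recurrence of QTcF prolongation (confirmed by central ECG lab) after reinitiation of study treatment at a reduced dose".

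Elsewhere, the note to Table 3-3 sends the reader to Section 3.3.1.1 for re-treatment after a hold. That section allows restart at a reduced dose once a possibly related toxicity has recovered to Grade 1 or baseline, and at an unchanged dose if the toxicity was unrelated.

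**The concern.** The hold rule and the second restart condition use the same thresholds in opposite directions. The first acts because the triplicate is over a threshold; the second requires that the excess was not confirmed. Since all the conditions must hold together, a patient held under the rule appears unable to restart under the list that follows it.

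At stake is a cardiac-safety decision for each affected patient, and that patient's exposure to both drugs. Section 3.3 stops cabozantinib and pembrolizumab together for a toxicity attributed to either, and removes patients after more than 6 weeks off both. A hold that the text gives no way to lift could therefore end pembrolizumab too.

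The recurrence trigger raises a second question: who performs the confirmation it calls for?

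**Working it through.** No sample size, power or alpha figure bears on this point, and the plan states no figure to reproduce. The check is one of logic.

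**1. Hold against restart condition 2.** Let B be baseline QTcF and A the triplicate average.

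- Hold mandated: A > 500, or A − B > 60.
- Condition 2: the value over those thresholds is not confirmed. With the triplicate as the confirmation step, this means A ≤ 500 and A − B ≤ 60.

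Each statement is the negation of the other, so no patient satisfies both. A hypothetical case: B = 440 and ECGs of 510, 510 and 500. A = 1520/3 = 506.7, and A − B = 66.7. The hold is mandatory and condition 2 fails.

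An enumeration over baselines of 380–500 ms and triplicates of 400–560 ms, in 10 ms steps, gave 19,118 combinations that mandate a hold. None of them meets condition 2. That zero follows from the definitions; it is not an estimate.

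**2. The case where condition 2 can be met.** In 9,493 further combinations the first ECG was over a threshold but the average was not. Example: B = 460 and ECGs of 510, 490 and 480, so A = 1480/3 = 493.3 and A − B = 33.3. Condition 2 is true, but the section mandates no hold. Restart becomes a question only if the investigator had already interrupted dosing.

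**3. Condition 2 against its neighbours.** Condition 3 counts a week from the return of QTcF, so QTcF must have been prolonged. Condition 4 asks for another cause of the prolongation, so there must be one to explain. The repeat-ECG schedule and the recurrence trigger both assume that some patients restart. Each fits a confirmed prolongation; condition 2 does not.

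**4. The section against 3.3.1.1.** For a possibly related toxicity that has recovered, 3.3.1.1 allows restart at a reduced dose. The QTc list requires a cause unequivocally other than cabozantinib. For an unrelated toxicity, 3.3.1.1 allows an unchanged dose; the QTc list speaks only of a reduced one. The protocol does not say which text governs.

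**5. Trigger against return clause.** Both are joined by an or. With B = 380 and QTcF = 450, the rise is 70 ms: over the trigger, yet already at or below 500. With B = 500, which the exclusion criteria admit, and QTcF = 510, the value is over 500 yet only 10 ms above baseline. On the same 10 ms grid, 42 of 13 × 17 = 221 baseline and QTcF pairs are over the trigger and within the return clause at once. Reading the clause as referring to whichever threshold was crossed would remove this, but the text does not say so.

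**6. Central ECG lab.** The recurrence trigger is the only mention. Section 2.5 names up to two sites. The study assessments table and its ECG footnote set a screening triplicate and routine on-treatment ECGs, with no transmission to or reading by a central laboratory. Section 25 lists ECG reports among the subjects' clinical source documents.

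**The case against.** Several stronger readings are tempting, and the documents do not support them.

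- **That no held patient can ever restart.** Section 3.3 lets the investigator interrupt cabozantinib for related adverse events at any time. A patient stopped on the first high ECG, with a triplicate average under both thresholds, meets condition 2. The contradiction is confined to holds mandated by the triplicate average.
- **That sites have no rule at all.** Section 3.3.1.1 gives general restart text. This stands, but it does not cure the conflict, because it sets different conditions from the specific list.
- **That permanent discontinuation depends on a central lab.** Either trigger suffices, and the cardiac-evaluation trigger needs no such lab.
- **That the trial has no central ECG lab.** This would be inference from silence. The most that can be said is that none is described elsewhere in the protocol as available.
- **That a recurrence would go unchecked.** The triplicate and hold rule applies at any time on study, so a recurrence on the triplicate again leads to withholding and sponsor notification. The lab wording bears on whether the stop becomes permanent.
- **That sites will act in opposite directions.** That is conjecture. There are at most two sites, and the QTc list requires sponsor agreement. That agreement is an added condition, however, not a waiver of the others.

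One could also argue that the confirmation meant in condition 2 is a later over-read of the local triplicate. That would make the list workable, but no such step is described. It is also unclear whether the list covers asymptomatic patients: it follows a sentence about patients with symptoms, and its first condition concerns symptoms.

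**Conclusion.** The point holds in a bounded form. For any hold mandated by the triplicate average, the restart list in Section 3.3.2.11 contradicts the trigger for that hold, and condition 2 also conflicts with conditions 3 and 4 and with the reinitiation text. This rests on one assumption: that the triplicate is the protocol procedure meant, which is the only one written. Separately, one of the two permanent-stop triggers relies on a central ECG lab that the protocol describes nowhere else.

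The number of patients affected is probably small but cannot be calculated. The section reports a mean rise of 10–15 ms at 140 mg with no value above 500 ms, and this trial starts at 40 mg. Against that, eligibility admits an average QTcF up to 500 ms, the same figure as the absolute threshold. No rate is given for a rise above 60 ms. The design for the primary endpoint is untouched. The point merits correction because a cardiac-safety rule cannot be followed as written.

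**What to change.** Reconcile the hold trigger, the restart list (including its return clause) and the permanent-stop list in Section 3.3.2.11 so that they can be applied together, and state which patients the restart list covers. Reconcile that section with the general restart text in Section 3.3.1.1 and say which governs. Reconcile the central-laboratory wording with the ECG procedures the trial actually uses, so that it is clear who confirms a recurrence.

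Whether, when or at what dose treatment should restart or stop is for the sponsor and investigators, and no position is taken on it here. The cost is a wording amendment to one section, with a cross-reference in a second. The sample size and the planned analyses do not change.

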3.3.2.12 Hypophosphatemia

Hypophosphatemia has been reported during treatment with cabozantinib. Serum phosphorus should be monitored frequently while receiving cabozantinib. Other causes of hypophosphatemia should be ruled out and/or these causes treated in accordance to standard of care. Mild to moderate hypophosphatemia should be managed by oral replacement including food that are high in phosphate (dairy items, meats, beans) and/or oral phosphate supplements in accordance to standard clinical practice guidelines.

Clinically relevant hypophosphatemia should be managed in accordance to the dose modification guidelines as outlined in Table 3-2 and Table 3-3 or as clinically indicated.

3.3.2.13 Thyroid Function Disorders

Changes in thyroid function tests (TFTs) and hypothyroidism have been reported with cabozantinib therapy and other tyrosine kinase inhibitors as a result of altered thyroid hormone regulation by mechanisms that seem to be specific for each agent (100). Currently available data are insufficient to determine the mechanism of TFT alterations and its clinical relevance. Routine monitoring of thyroid function and assessments for signs and symptoms associated with thyroid dysfunction is recommended before initiation and during treatment with cabozantinib.

Management of thyroid dysfunction (eg, symptomatic hypothyroidism) should follow accepted clinical practice guidelines and dose modification guidelines as outlined in Table 3-2 and Table 3-3.

3.3.2.14 Hemorrhagic Events

Hemorrhagic events have been reported with cabozantinib. In order to mitigate risk of severe hemorrhage, subjects should be evaluated for potential bleeding risk factors before initiating cabozantinib treatment and monitored for bleeding events with serial complete blood counts and physical examination while on study. Risk factors for hemorrhagic events may include (but may not be limited to) the following:

- Tumor of the lung with cavitary lesions or tumor lesions which invades, encases, major blood vessels. The anatomic location and characteristics of tumor as well as the medical history must be carefully reviewed in the selection of subjects for treatment with cabozantinib;
- Recent or concurrent radiation to the thoracic cavity;
- Active peptic ulcer disease, inflammatory GI diseases including Crohn's disease and ulcerative colitis;
- Underlying medical conditions which affect normal hemostasis (eg, deficiencies in clotting factors and/or platelet function, or thrombocytopenia);
- Concomitant medication with anticoagulants or other drugs which affect normal hemostasis;
- History of clinically significant hemoptysis.

The risk of hemorrhage in cabozantinib-treated subjects with brain metastases has not been thoroughly analyzed. Though the incidence of CNS hemorrhage events in a study of subjects with GB was higher than observed in general population of subjects with cancer treated with cabozantinib, it is not clear how the risk of hemorrhage in GB translates to a risk of hemorrhage for subjects with brain metastases. Currently, brain metastases of carcinomas are not contraindications to the use of cabozantinib, but subjects with brain metastases should be monitored with a high index of suspicion if symptoms that could be due to a CNS hemorrhage occur.

Cabozantinib should be discontinued in subjects with serious and life-threatening bleeding events or recent hemoptysis (≥ 2.5 mL of red blood).

3.3.2.15 GI Perforation/Fistula and Non-GI Fistula Formation

Gastrointestinal perforation/GI fistula: Prior to initiation of treatment with cabozantinib, subjects should be carefully evaluated for potential risk factors including (but not limited to) the following:

- Tumors invading GI or respiratory tracts
- Active peptic ulcer disease, inflammatory bowel disease (eg, ulcerative colitis, Crohn's disease), diverticulitis, cholecystitis or symptomatic cholangitis, or appendicitis
- History of abdominal fistula, GI perforation, bowel obstruction, or intra-abdominal abscess
- Ongoing visceral complications from prior radiation therapy
- Prior GI surgery (particularly when associated with delayed or incomplete healing)

Complete healing following abdominal surgery and/or resolution of intra-abdominal abscess must be confirmed prior to initiating treatment with cabozantinib.

After starting cabozantinib, subjects should be monitored for early signs of GI perforation such as abdominal pain, nausea, emesis, constipation, and fever especially if known risk factors for developing GI perforation or fistula are present.

Discontinue cabozantinib treatment in subjects who have been diagnosed with GI perforation/fistula.

Non-GI fistula formation: Complications from radiation therapy has been identified as a possible predisposing risk factor for fistula formation in subjects undergoing treatment with cabozantinib.

Subjects with any clinically relevant ongoing complications from prior radiation therapy (ie, radiation esophagitis or other inflammation of the viscera) should not be treated with cabozantinib.

Radiation therapy to the thoracic cavity (including mediastinum) should be avoided within 3 months of starting treatment with cabozantinib (excluding local radiation for bone metastases). Fistula should be ruled out as appropriate in cases of onset of severe mucositis or difficulty swallowing after start of therapy. Discontinue cabozantinib and initiate appropriate management in subjects who have been diagnosed with a non-GI fistula.

Discontinue cabozantinib treatment in subjects who have been diagnosed with non-GI fistula.

3.3.2.16 Osteonecrosis of the Jaw

Osteonecrosis of the jaw (ONJ) has been reported in subjects treated with cabozantinib. Additional risk factors for ONJ have been identified including the use of bisphosphonates and denosumab, chemotherapy, corticosteroids, local radiotherapy, and dental or orofacial surgery procedures.

Osteonecrosis of the jaw can manifest as jaw pain, osteomyelitis, osteitis, bone erosion, tooth or periodontal infection, toothache, gingival ulceration, or gingival erosion. Persistent pain or slow healing of the mouth or jaw after dental surgery may also be manifestations of ONJ.

Perform an oral examination prior to initiation of cabozantinib and periodically during cabozantinib therapy. Advise subjects regarding oral hygiene practice and to quickly report symptoms to investigator. Caution should be used in subjects receiving bisphosphonates.

Invasive dental procedures should be avoided. In cases where dental procedures are unavoidable, treatment with cabozantinib should be held for at least 4 weeks prior to the procedure and resumed after complete wound healing has occurred. Bone healing may often require a protracted time.

3.3.2.17 Angioedema

Angioedema should be managed according to standard practice. The subject should be observed until symptoms resolve, with particular attention to maintaining an open airway.

3.3.2.18 Musculoskeletal and Connective Tissue Disorders

Cabozantinib appears to represent minimal risk of adverse musculoskeletal effects based on nonclinical GLP-compliant toxicology studies. The development of new or progressive, unexplained musculoskeletal symptoms such as pain or weakness should be assessed for underlying causes.

Rhabdomyolysis has been reported. Cabozantinib should be discontinued in subjects with serious and life-threatening rhabdomyolysis and interrupted if less severe forms occur when there are no other clear causes. Reinitiation of cabozantinib treatment must be discussed with and approved by the sponsor. Therapy of rhabdomyolysis should include supportive care and standard medical intervention.

A diagnosis of reversible posterior leukoencephalopathy syndrome requires permanent discontinuation of cabozantinib.

3.3.2.19 Respiratory, Thoracic and Mediastinal Disorders

Dyspnea has been reported in clinical studies with cabozantinib. Symptoms should be managed according to locally accepted clinical practice including an assessment for underlying causes. Pulmonary embolism should be considered as possible causes for new onset dyspnea given the risk of thrombosis associated with inhibition of VEGF signaling. Furthermore, fistula formation (Section 0) and pneumonia have been reported in subjects treated with cabozantinib and should be considered as clinically indicated in subjects presenting with pulmonary symptoms.

3.4 Concomitant Medications and Therapies

3.4.1 Anticancer Therapy

Local intervention is discouraged unless medically unavoidable. Subjects receiving local intervention (eg, palliative radiation) are allowed to continue to receive study treatment at the investigator's discretion.

Pembrolizumab Drug information:

Brand Names: US

Keytruda

Dosing: Adult

Head and neck cancer, squamous cell, recurrent or metastatic:

IV: 200 mg once every 3 weeks until disease progression, unacceptable toxicity, or (in patients without disease progression) for up to 24 months.

Dosing: Geriatric

Refer to adult dosing.

Dosing: Renal Impairment

No dosage adjustment necessary. In a pharmacokinetic study, no difference in clearance was noted for patients with eGFR ≥ 15 mL/minute/1.73 m².

Dosing: Hepatic Impairment

Hepatic impairment prior to treatment initiation:

Mild impairment (total bilirubin \leq ULN and AST $>$ ULN or total bilirubin $>$ 1 to 1.5 times ULN and any AST): No dosage adjustment necessary.

Moderate (total bilirubin $>$ 1.5 to 3 times ULN and any AST) to severe (total bilirubin $>$ 3 times ULN and any AST) impairment: There are no dosage adjustments provided in the manufacturer's labeling (has not been studied).

Hepatotoxicity during treatment:

Note: For patients with baseline grade 2 ALT or AST abnormalities due to liver metastases, permanently discontinue if AST or ALT increases by $\geq 50\%$ (relative to baseline) and persists at least 1 week.

AST or ALT $>$ 3 to 5 times ULN or total bilirubin $>$ 1.5 to 3 times ULN: Withhold treatment; may resume therapy upon recovery to grade 0 or 1 toxicity. Also administer corticosteroids (prednisone 0.5 to 1 mg/kg/day [or equivalent] followed by a taper).

AST or ALT $>$ 5 times ULN or total bilirubin $>$ 3 times ULN: Permanently discontinue. Also administer corticosteroids (prednisone 1 to 2 mg/kg/day [or equivalent] followed a taper).

Ocular toxicity: Optic neuritis which could manifest as a sudden onset of vision loss, loss of color vision, pain when moving eyes, and/or loss of peripheral vision. It may affect one or both eyes at the same time (optic neuritis).

Dosing: Adjustment for Toxicity

Withhold treatment for any of the following (may resume upon recovery to grade 0 or 1 toxicity):

Colitis, moderate (grade 2) or severe (grade 3); also administer corticosteroids (prednisone 1 to 2 mg/kg/day [or equivalent] followed by a taper).

Endocrinopathies:

Hyperglycemia, severe (Grade 3); also administer antihyperglycemics.

Hyperthyroidism, severe (grade 3) or life threatening (grade 4); manage with thionamides and beta-blockers as appropriate.

Hypophysitis, grade 2 (symptomatic); also administer corticosteroids (followed by a taper) and hormone replacement therapy if appropriate.

Hypoparathyroidism (Low levels of parathyroid hormone) (may occur rarely (<1%) which may result in low blood calcium and cause muscle cramps or spasms; fatigue or weakness; numbness, tingling or burning in fingertips, toes or lips

Nephritis, grade 2; also administer corticosteroids (prednisone 1 to 2 mg/kg/day [or equivalent] followed by a taper).

Pneumonitis, moderate (grade 2); also administer corticosteroids (prednisone 1 to 2 mg/kg/day [or equivalent] followed by a taper).

Other treatment-related toxicity, severe or grade 3; may require corticosteroids (based on severity). Upon improvement to grade 0 or 1, initiate corticosteroid taper and continue to taper over at least 1 month. Restart pembrolizumab if the adverse reaction remains at grade 0 or 1 following corticosteroid taper. May consider other systemic immunosuppressants if not controlled by corticosteroids (based on limited data).

Withhold (may resume upon recovery to grade 0 or 1 toxicity) or discontinue for:

Hyperthyroidism, severe (grade 3) or life-threatening (grade 4); manage with thionamides and beta-blockers as appropriate.

Hypophysitis, severe (grade 3) or life-threatening (grade 4); also administer corticosteroids and hormone replacement as appropriate.

Permanently discontinue for:

Adverse reactions that are life-threatening, persistent grade 2 or 3 adverse reaction (excluding endocrinopathies controlled with hormone replacement therapy) that does not recover to grade 0 or 1 within 12 weeks after the last pembrolizumab dose, or any recurrent severe or grade 3 treatment-related adverse reaction. Also administer corticosteroids (may consider other systemic immunosuppressants if not controlled by corticosteroids [based on limited data]).

Colitis, life-threatening (grade 4); also administer corticosteroids (prednisone 1 to 2 mg/kg/day [or equivalent] followed by a taper).

Immune mediated adverse reactions: Discontinue permanently if unable to reduce corticosteroid dose to prednisone \leq 10 mg/day (or equivalent) within 12 weeks.

Infusion-related reaction, grade 3 or 4.

Nephritis, severe (grade 3) or life-threatening (grade 4); also administer corticosteroids (prednisone 1 to 2 mg/kg/day [or equivalent] followed by a taper).

Pneumonitis, severe (grade 3), life-threatening (grade 4), or moderate (grade 2) that recurs; also administer corticosteroids (prednisone 1 to 2 mg/kg/day [or equivalent] followed by a taper).

Dosage Forms: US

Excipient information presented when available (limited, particularly for generics); consult specific product labeling.

Solution, Intravenous [preservative free]:

Keytruda: 100 mg/4 mL (4 mL) [contains polysorbate 80]

Solution Reconstituted, Intravenous [preservative free]:

Keytruda: 50 mg (1 ea) [contains polysorbate 80]

Medication Guide and/or Vaccine Information Statement (VIS)

An FDA-approved patient medication guide, which is available with the product information and at <http://www.fda.gov/downloads/Drugs/DrugSafety/UCM417493.pdf>, must be dispensed with this medication.

Administration

IV: Infuse over 30 minutes through a 0.2 to 5 micron sterile, nonpyrogenic, low-protein binding inline or add-on filter. Do not infuse other medications through the same infusion line. Would allow a 10 minutes window of infusion duration.

Use

Melanoma, unresectable or metastatic: Treatment of unresectable or metastatic melanoma.

Non-small cell lung cancer, metastatic: Treatment of metastatic non-small cell lung cancer in patients with PD-L1-expressing tumors (as determined by an approved test) who have disease progression on or after platinum-containing chemotherapy. Patients with EGFR or ALK genomic tumor aberrations should have disease progression (on approved EGFR- or ALK-directed therapy) prior to receiving pembrolizumab.

Head and neck cancer, squamous cell, recurrent or metastatic: Treatment of recurrent or metastatic squamous cell carcinoma of the head and neck in patients with disease progression on or after platinum-containing chemotherapy.

Adverse Reactions Significant

Incidence of adverse reactions include unapproved dosing regimens.

>10%:

Cardiovascular: Peripheral edema (10%)

Central nervous system: Fatigue (43% to ≤44%)

Dermatologic: Pruritus (12% to 28%), skin rash (18% to 24%; immune-mediated <1%)

Endocrine & metabolic: Hyperglycemia (48% to 49%; grades 3/4: 3% to 6%), hyponatremia (37% to 38%), hypoalbuminemia (32% to 37%), hypertriglyceridemia (23% to 33%), decreased serum bicarbonate (22%), hypocalcemia (21%), hypercholesterolemia (20%)

Gastrointestinal: Decreased appetite (20% to 25%), nausea (18% to 22%), constipation (15% to 22%), diarrhea (15% to 20%), abdominal pain (13%), vomiting (12% to 13%)

Hematologic & oncologic: Anemia (12% to 44%; grades 3/4: ≤10%), lymphocytopenia (40%; grades 3/4: 9%)

Hepatic: Increased serum alkaline phosphatase (26%), increased serum AST (20% to 24%; grades 3/4: 1% to 2%), increased serum ALT (21%; grades 3/4: 2%)

Neuromuscular & skeletal: Weakness (10% to ≤44%), arthralgia (14% to 15%)

Respiratory: Cough (18% to 29%), dyspnea (23%)

Miscellaneous: Fever (12% to 14%)

1% to 10%:

Cardiovascular: Pulmonary embolism ($\geq 2\%$)

Central nervous system: Peripheral neuropathy (2%)

Endocrine & metabolic: Hypothyroidism (immune-mediated; 7% to 8%), hyperthyroidism (immune-mediated; 2% to 3%; grade 2: <1%; grade 3: <1%)

Gastrointestinal: Colitis (immune-mediated; $\leq 2\%$; grade 2: <1%, grade 3: <1%)

Neuromuscular & skeletal: Back pain (10%)

Respiratory: Pneumonitis (2% to 4%; grade 2: $\leq 1\%$; grade 3: $\leq 1\%$; grade 4: <1%), pleural effusion ($\geq 2\%$), pneumonia ($\geq 2\%$)

<1% (Limited to important or life-threatening): Adrenocortical insufficiency (immune-mediated), antibody development, arthritis (immune-mediated), bullous pemphigoid (immune-mediated), chronic inflammatory demyelinating polyradiculoneuropathy, diabetic ketoacidosis, exfoliative dermatitis (immune-mediated), Guillain-Barré syndrome (immune-mediated), hemolytic anemia (immune-mediated), hepatitis (including autoimmune hepatitis), hypophysitis, infusion-related reaction, interstitial nephritis (with renal failure), Lambert-Eaton syndrome (immune-mediated), myasthenia gravis (immune-mediated), myositis (immune-mediated), nephritis (autoimmune), optic neuritis (immune-mediated), pancreatitis (immune-mediated), partial epilepsy (immune-mediated; in a patient with inflammatory foci in brain parenchyma), rhabdomyolysis (immune-mediated), serum sickness (immune-mediated), severe dermatitis, type 1 diabetes mellitus, uveitis (immune-mediated), vasculitis (immune-mediated)

New identified risk of myelitis has been added to the safety profile of Pembrolizumab

Contraindications

There are no contraindications listed in the manufacturer's US labeling.

Canadian labeling: Hypersensitivity to pembrolizumab or any component of the formulation.

Warnings/Precautions

Concerns related to adverse effects:

AEs associated with pembrolizumab exposure, including coadministration with additional compounds, may represent an immunologic aetiology. These immune-related AEs (irAEs) may

occur shortly after the first dose or several months after the last dose of pembrolizumab/combination treatment and may affect more than one body system simultaneously. Therefore, early recognition and initiation of treatment is critical to reduce complications. Based on existing clinical study data, most irAEs were reversible and could be managed with interruptions of pembrolizumab/combination treatment, administration of corticosteroids and/or other supportive care. For suspected irAEs, ensure adequate evaluation to confirm etiology or exclude other causes. Additional procedures or tests such as bronchoscopy, endoscopy, skin biopsy may be included as part of the evaluation.

- Diabetes mellitus: Type 1 diabetes mellitus has occurred (including diabetic ketoacidosis). Monitor closely for hyperglycemia and other signs/symptoms of diabetes. Insulin therapy may be required; if severe hyperglycemia is observed (Grade 3), administer antihyperglycemics and withhold pembrolizumab treatment until glucose control has been accomplished.
- Gastrointestinal toxicity: Immune-mediated colitis has occurred, including cases of grade 2 to 4 colitis. The median time to onset of colitis was 3.4 months (range: 10 days to ~10 months) and the median duration was 1.4 months (range: 1 day to ~7 months) in patients with melanoma. In patients with NSCLC, the median time to onset was 1.6 months (range: ~1 to ~2 months) and the median duration was 16 days (range: 1 to ~6 weeks). In some melanoma patients, colitis was managed with high-dose systemic corticosteroids for a median duration of 6 days (range: 1 day to 5.3 months), followed by a corticosteroid taper. Most patients with colitis experienced complete resolution. May require treatment interruption, systemic corticosteroid therapy, and/or permanent discontinuation. Monitor for signs and symptoms of colitis; administer systemic corticosteroids for grade 2 or higher colitis.
- Hepatotoxicity: Immune-mediated hepatitis occurred (grades 2 to 4 hepatitis). The median onset for hepatitis was 26 days (range: 8 days to 21.4 months); the median duration was 1.2 months (range: 8 days to 4.7 months). Hepatitis resolved in most patients. Administer corticosteroids (prednisone 0.5 to 1 mg/kg/day [or equivalent] for grade 2 hepatitis, and prednisone 1 to 2 mg/kg/day [or equivalent] for grade 3 or higher, each followed by a taper), and withhold or discontinue therapy based on the severity of liver enzyme elevations. The median duration of high-dose corticosteroid therapy was 5 days (range: 1 to 14 days) followed by a taper. Monitor for liver function changes. May require treatment interruption, systemic corticosteroids (for grade 2 or higher toxicity), and/or permanent discontinuation.

- Hypophysitis: Immune-mediated hypophysitis occurred (grades 2, 3, and 4). In patients with melanoma, the median time to onset was 3.3 months (range: 1 days to 7.2 months) and the median duration was 2.7 months (range 12 days to 12.7 months). The time to onset in NSCLC (1 patient) was 3.7 months. Monitor for signs/symptoms of hypophysitis (eg, hypopituitarism, adrenal insufficiency). May require treatment interruption, systemic corticosteroids and hormone replacement therapy (as clinically indicated), and/or permanent discontinuation.
- Infusion-related reactions: Infusion-related reactions (including severe and life-threatening cases) have occurred. Monitor for signs/symptoms of a reaction (eg, rigors, chills, wheezing, pruritus, flushing, rash, hypotension, hypoxemia, and fever). Interrupt infusion and permanently discontinue for severe (grade 3) or life-threatening (grade 4) infusion-related reactions.
- Nephrotoxicity: Immune-mediated nephritis has occurred. The onset for autoimmune nephritis in melanoma patients was 5.1 months (range: 12 days to 12.8 months) and the median duration was 1.1 months (range: 3 days to 3.3 months). Grade 2 or higher nephritis should be managed with systemic corticosteroids (prednisone initial dose of 1 to 2 mg/kg/day [or equivalent], followed by a taper). The median duration of corticosteroid use was 15 days (range: 3 days to 1.6 months), followed by a taper. Nephritis resolved in some patients. Monitor for renal function changes. May require treatment interruption, systemic corticosteroids (for grade 2 or higher toxicity), and/or permanent discontinuation.
- Pulmonary toxicity: Immune-mediated pneumonitis has been observed, including fatal cases. For patients with melanoma, the median time to development was 4.3 months (range: ~2 days to ~19 months) and the median duration was 2.6 months (range: 2 days to ~15 months). Some patients required initial management with high-dose systemic corticosteroids, the median duration of initial corticosteroid therapy was 8 days (range: 1 to 34 days) followed by a corticosteroid taper. Pneumonitis completely resolved in nearly two-thirds of melanoma patients. For patients with NSCLC, the median time to development was 1.7 months (range: 4 days to ~13 months) and the median duration was 1.2 months (range: 5 days to ~12 months). Some NSCLC patients had complete resolution of pneumonitis. May require treatment interruption, corticosteroid therapy (prednisone 1 to 2 mg/kg /day [or equivalent] followed by a taper, for grade 2 or higher pneumonitis), and/or permanent discontinuation. Monitor for signs and symptoms of pneumonitis; if pneumonitis is suspected, evaluate with radiographic imaging and administer systemic corticosteroids for grade 2 or higher pneumonitis. For NSCLC, pneumonitis occurred more frequently in patients with a history of asthma, COPD, or prior thoracic radiation.

- Thyroid disorders: Immune-mediated hyperthyroidism and hypothyroidism have occurred. The median onset for hyperthyroidism was 1.4 to 1.8 months (range: 1 day to ~22 months), and the median duration was 1.7 to 4.5 months (range: 1 day to ~13 months). Hyperthyroidism resolved in over two-thirds of melanoma patients. Hypothyroidism occurred with a median onset of 3.3 to 4.2 months (range: 5 days to 19 months) and median duration of 5.4 to 5.84 months (range: 6 days to 24.3 months), and occurred in some patients with no prior history of thyroid disorders. Hypothyroidism was generally managed with long-term thyroid hormone replacement therapy, although some patients only required short-term replacement therapy. Hypothyroidism did not require systemic corticosteroid therapy or discontinuation. Thyroid disorders may occur at any point in pembrolizumab therapy. Monitor for changes in thyroid function (at baseline, periodically during treatment and as clinically indicated) and for signs/symptoms of thyroid disorders. Administer thionamides and beta-blockers for hyperthyroidism as appropriate; may require treatment interruption and/or permanent discontinuation. Isolated hypothyroidism may be managed with replacement therapy (without corticosteroids and treatment interruption).
- Other immune-mediated toxicities: Other clinically relevant immune-mediated disorders have been observed, including rash, exfoliative dermatitis, bullous pemphigoid, uveitis, arthritis, vasculitis, myositis, Guillain-Barré syndrome, pancreatitis, hemolytic anemia, serum sickness, myasthenia gravis, and partial seizures (in a patient with inflammatory foci in brain parenchyma). If an immune-mediated adverse event is suspected, evaluate appropriately to confirm or exclude other causes; withhold treatment and administer systemic corticosteroids based on severity of reaction. Upon resolution to grade 0 or 1, initiate corticosteroid taper (continue tapering over at least 1 month). When reaction remains at grade 1 or less during taper may reinitiate pembrolizumab. Immune-mediated adverse reactions that do not resolve with systemic corticosteroids may be managed with other systemic immunosuppressants (based on limited data). Discontinue permanently for severe or grade 3 immune-mediated adverse event that is recurrent or life-threatening.

Pregnancy Implications

